9.2 Analysis Sets

The following analysis sets will be used in this study:

- Enrolled: Subjects who sign informed consent and are assigned a subject identification number
- Full: Subjects in the enrolled analysis set who receive a randomized treatment group assignment (rimegepant or placebo)
- Double-blind treatment safety: Subjects in the enrolled analysis set who take ≥ 1 dose of double-blind study drug (rimegepant or placebo)
- Open-label rimegepant safety: Subjects in the enrolled analysis set who take ≥ 1 dose of open-label rimegepant
- Double-blind or open-label rimegepant safety: Subjects in the enrolled analysis set who take
 ≥ 1 dose of double-blind or open-label rimegepant
- Double-blind treatment efficacy: Subjects in the full analysis set who are randomized only
 once, and take ≥ 1 dose of double-blind study drug
- Migraine: Subjects in the double-blind treatment efficacy analysis set with ≥ 14 days of eDiary efficacy data (not necessarily consecutive) in both the Observation Phase and ≥ 1 month (4-week interval) in the Double-blind Treatment Phase

9.3 Statistical Methods

Results will be summarized by treatment group.

9.3.1 Efficacy Analyses

9.3.1.1 Primary Efficacy Endpoint

The primary endpoint will be assessed for the migraine analysis set using a linear mixed effects model with repeated measures that will include the following variables: change from the Observation Phase in the number of migraine days per month as the dependent variable; number of migraine days per month in the Observation Phase as a covariate; and fixed effects for treatment group, randomization stratum (i.e., use of prior prophylactic migraine medication generally considered to have efficacy), month, and month-by-treatment group interaction. Migraine days are of any pain intensity. Months are defined using 4-week intervals as Month 1 (Weeks 1 to 4), Month 2 (Weeks 5 to 8), and Month 3 (Weeks 9 to 12). The number of migraine days per month is prorated to 28 days account for days with missing migraine data. The difference estimate (rimegepant – placebo), standard error (SE), p-value and 97.5% confidence interval (CI) will be reported for the entire Double-blind Treatment Phase (Weeks 1 to 12) for each rimegepant treatment group versus placebo.

The repeated measures error structure is assumed to be constant across treatment groups and will be initially specified as unstructured. If the model fails to converge or cannot be fit with an unstructured error structure, then a heterogeneous Toeplitz error structure will be attempted. If the Toeplitz fails, then an autoregressive order 1 error structure will be attempted.

The Huber-White robust "sandwich" estimator will be used for the estimation of SEs, which does not require constant response variances between treatment groups and different baseline covariate values.

9.3.1.2 Secondary Efficacy Endpoints

The proportion of subjects with ≥ 50% reduction from the Observation Phase in the number of moderate or severe migraine days per month over the entire Double-blind Treatment Phase (Weeks 1 to 12) will be analyzed using Mantel-Haenszel risk estimation with stratification by randomization stratum for the migraine analysis set. Missing data are imputed as non-response (i.e., failure). The difference estimate (rimegepant – placebo), SE, p-value and 97.5% CI will be reported for each rimegepant treatment group versus placebo.

The mean change from the Observation Phase in the number of migraine days per month in the last 4 weeks (Weeks 9 to 12) of the Double-blind Treatment Phase will be assessed for the migraine analysis set from the same model used for the primary efficacy endpoint.

The mean change from the Observation Phase in the number of migraine days per month in the first 4 weeks (Weeks 1 to 4) of the Double-blind Treatment Phase will be assessed for the migraine analysis set from the same model used for the primary efficacy endpoint.

The mean number of acute migraine-specific medication days per month over the entire Doubleblind Treatment Phase (Weeks 1 to 12) will be assessed for the migraine analysis set using a model that is similar in structure to that used for the primary efficacy endpoint, except that the number of acute migraine-specific medication days per month is the dependent variable and there is no covariate. Acute migraine-specific medications are triptans and ergotamine.

The mean change from baseline in the MSQ restrictive role function domain score at Week 12 will be analyzed for the double-blind treatment efficacy analysis set using a linear model that will include the following variables: Week 12 change from baseline in the score as the dependent variable; baseline score as a covariate; and fixed effects for treatment group and randomization stratum. The Week 12 difference estimate (rimegepant – placebo), SE, p-value and 97.5% CI will be reported for each rimegepant treatment group versus placebo.

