6.3 Efficacy Assessments

The eDiary will be used daily to record acute medication dosing occurrences (i.e., with triptans, ergotamine, or other), and migraine pain features and associated symptoms during the Observation Phase and the Double-blind Treatment Phase.

Efficacy assessments will be derived from eDiary data and will include the number of migraine days per month by pain intensity (total; moderate or severe), and number of acute migraine-specific medication days per month, in each month by study period. Please refer to Table 1.

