 - O Migraine: subjects in the DBT efficacy analysis set with ≥ 14 days of eDiary efficacy data (not necessarily consecutive) in both the OP and ≥ 1 month (4-week interval) in the DBT Phase (see Section 6.3.1). This analysis set is used to assess migraine days, acute migraine-specific medication days, acute migraine medication days, and headache days.
 - o First month migraine: subjects in the DBT efficacy analysis set with ≥ 24 days of eDiary efficacy data (not necessarily consecutive) in both the OP and in first month (4-week interval) of the DBT Phase (see Section 6.3.3.3). This analysis set is used to assess efficacy endpoints per week.
 - o First week treated migraine: subjects in the DBT efficacy analysis set with (1) ≥ 24 days of eDiary efficacy data in the OP (not necessarily consecutive), (2) 7 consecutive days of eDiary efficacy data in the first week of the DBT Phase, and (3) 7 consecutive days of DB study drug dosing in the first week of the DBT Phase (see Section 6.3.3.5). This analysis set is used to assess efficacy endpoints per day.

See Section 7.1 for derived dates and Section 7.2 for analysis periods.

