6.2.5.2 Baseline Disease Characteristics

Migraine History

Refer to the Core SAP for the table of migraine history.

Cardiac and Other Risk Factors

Refer to the Core SAP for the frequency table of cardiac and other risk factors. This table is provided only for the DBT safety analysis set.

Migraine-Related Event Days During the OP

The table of migraine-related event days per month during the OP is provided only for the migraine analysis set, and summarizes the following efficacy parameters descriptively as continuous or categorical variables during the OP analysis period:

- Migraine days per month by pain intensity (total; moderate or severe). Categories are $< 6, \ge 6$ to $< 8, \ge 8$ to $< 12, \ge 12$.
- Headache days per month by pain intensity (total; moderate or severe). Categories are same as for migraine days per month above.
- Acute migraine-specific medication days per month. Categories are 0, > 0 to < 2, ≥ 2 to < 4, ≥ 4 to < 6, ≥ 6 to < 8, ≥ 8 to ≤ 14, > 14. Acute migraine medication days per month. Categories are the same as for acute migraine-specific medication days per month, listed above. The table of migraine related event days per week during the OP is provided only for the first month migraine analysis set, and summarizes the following efficacy parameters descriptively as continuous or categorical variables during the OP analysis period:
- Migraine days per week by pain intensity (total; moderate or severe). Categories are $< 1, \ge 1$ to $< 2, \ge 2$ to $< 3, \ge 3$.
- Headache days per week by pain intensity (total; moderate or severe). Categories are same as for migraine days per week above.

See Section 6.3.1 for migraine days per month, Section 6.3.3.1 for headache days per month, Section 6.3.3.3 for migraine days per week and headache days per week, Section 6.3.2.2 for acute migraine-specific medication days per month, Section 6.3.3.6 for acute migraine medication days per month, and Section 7.2 for the OP analysis period.

Categories may be redefined or combined based on the availability of the data.

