6.3.2.2 Acute Migraine-Specific Medication Days per Month Over Time on DBT

During the DBT Phase, subjects may record taking triptan, ergotamine, and other medications to treat headache or aura yesterday in the eDiary headache report.

Pfizer Confidential

Acute migraine-specific medication days per month are assessed as "acute migraine-specific medication days per 4 weeks" to correspond with the 4-week visit schedule. Acute migraine-specific medication days per month are based = on 4-week intervals. See Section 9.2.4 for the definition of acute migraine-specific medication days.

Analyses are based on the migraine analysis set with eDiary efficacy dates in the on-DBT efficacy analysis period.

The number of acute migraine-specific medication days per month in the DBT Phase is prorated to 28 days and derived as follows:

- Month (i.e., 4-week interval) in the on-DBT efficacy analysis period: 28 × (total number of acute migraine-specific medication days in the month)/(total number of eDiary efficacy data days in the month). Subjects must have ≥ 14 days of eDiary efficacy data (not necessarily consecutive) in the specified month to be evaluable.
- Overall DBT: 28 × (total number of acute migraine-specific medication days through Month 3 in the on-DBT efficacy analysis period)/(total number of eDiary efficacy data days through Month 3 in the on-DBT efficacy analysis period).

Descriptive Analyses

The table of the number of acute migraine-specific medication days per month in the DBT analysis period is provided, and summarizes the parameter descriptively as a continuous variable by treatment group in each month of the DBT Phase and overall DBT.

Treatment Group Comparisons

Treatment groups are compared using a linear mixed effects model with repeated measures and the following attributes:

- Variables: number of acute migraine-specific medication days per month as the dependent variable; treatment group, randomization stratum, month (i.e., Months 1 to 3 of the DBT Phase), and the month-by-treatment group interaction as fixed effects
- Covariance structure for repeated measures accounting for within-subject correlated errors : See Section 6.3.1.3.
- SE estimation method: See Section 6.3.1.3.

The table displays the following model estimates:

- LSM, SE, and 97.5% CI by month and overall DBT for each treatment group

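### The fourth key secondary endpoint, acute migraine-specific medication days, is analysed without its Observation Phase value, which is on record for every subject analysed; the test is valid but less precise than it could be.

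*Protocol*

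**What the plan says.** Protocol 9.3.1.2 takes over the structure of the primary model for this endpoint, except that "the number of acute migraine-specific medication days per month is the dependent variable and there is no covariate". SAP 6.3.2.2 matches it: "Variables: number of acute migraine-specific medication days per month as the dependent variable; treatment group, randomization stratum", followed by month and the treatment-by-month interaction. No OP term appears.

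The OP value is nevertheless available:

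- Protocol 6.3: "The eDiary will be used daily to record acute medication dosing occurrences", in the Observation Phase as well as on treatment. SAP 6.3.1 confirms daily recording in both phases.
- SAP 4.1: membership of the migraine analysis set requires "≥ 14 days of eDiary efficacy data (not necessarily consecutive) in both the OP and ≥ 1 month" on treatment. SAP 9.2.4 derives a medication day from those same diary days, so every member has an evaluable OP value.
- SAP 6.2.5.2: "The table of migraine-related event days per month during the OP is provided only for the migraine analysis set", and one of its rows is "Acute migraine-specific medication days per month. Categories are 0", with bands running up to more than 14 days.

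For the derivation, that section points to "Section 6.3.2.2 for acute migraine-specific medication days per month" and to SAP 7.2 for the OP analysis period. SAP 6.3.2.2 announces its formulas thus: "The number of acute migraine-specific medication days per month in the DBT Phase is prorated to 28 days and derived as follows". It then gives a monthly and an overall formula, both on treatment only.

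**The concern.** Every other continuous endpoint in the testing hierarchy is adjusted for its own pre-treatment value. The primary, last-month and first-month endpoints share a model with OP migraine days as covariate, and the MSQ model has the baseline score. Only this endpoint leaves between-subject differences in habitual triptan use, beyond what stratum explains, in the error term.

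The plan consistently treats the endpoint as an on-treatment level rather than a change (SAP 6.3.2.3). That does not explain the omission. In a randomized comparison, a level can be adjusted for its OP value and the target is still the same difference in means.

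What is at stake is the width of the confidence interval and the chance of passing the fourth gate. Under Protocol 9.3.1.3 and SAP 5, if a regimen succeeds on the primary and the first three secondaries, a miss here also ends formal testing of MSQ for that regimen.

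**Working it through.** **1. The plan's own figure.** The only stated power is for the primary endpoint: roughly 80% with 200 per arm, a 1.1-day difference, SD 3.5 and two-sided alpha 0.025 (Protocol 9.1, SAP 5). The standard error is 3.5 × sqrt(2/200) = 0.35, so z = 1.1/0.35 = 3.143. Power = Φ(3.143 - 2.241) = 0.816, which agrees. No SD, effect or power is stated for the fourth secondary.

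**2. Closed form.** Let rho be the within-arm correlation of the OP value with the 12-week on-treatment value, after adjusting for stratum. Treating the 12-week mean as one outcome, the covariate multiplies the residual variance by 1 - rho². So:

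- SE multiplier = sqrt(1 - rho²).
- An adjusted analysis needs only 200 × (1 - rho²) per arm to match the planned one, so the omission wastes 200 × rho² subjects per arm.

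The documents do not give rho. It is assumed over a range:

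| rho (assumed) | SE multiplier | Equivalent subjects lost per arm |
|---|---|---|
| 0.1 | 0.995 | 2 |
| 0.2 | 0.980 | 8 |
| 0.3 | 0.954 | 18 |
| 0.4 | 0.917 | 32 |
| 0.5 | 0.866 | 50 |
| 0.6 | 0.800 | 72 |
| 0.7 | 0.714 | 98 |

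**3. Allowing for stratum.** Stratum is already in the model, so a raw correlation overstates the gain. If stratum correlates a with both values, partial = (raw - a²)/(1 - a²). At a = 0.3, raw 0.3, 0.5 and 0.7 become (0.30 - 0.09)/0.91 = 0.23, (0.50 - 0.09)/0.91 = 0.45 and (0.70 - 0.09)/0.91 = 0.67, or about 11, 41 and 90 subjects per arm. At a = 0.2 they become 0.27, 0.48 and 0.69, or about 15, 46 and 95.

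**4. In terms of power.** If the planned test had 80% power (assumed), it would have 84%, 91% and 98% with the covariate at rho 0.3, 0.5 and 0.7. From an assumed 60%, it would have 65%, 74% and 90%.

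**5. Simulation check.** All inputs are assumed: three arms of 200, 30% in one stratum with a log-rate shift of 0.2, 70% users, Poisson counts on log-normal rates (log-SD 0.6) capped at 28, mean of three complete months, no treatment effect, sandwich SE, 3000 runs per row.

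| Partial rho | Predicted SE ratio | Mean robust SE ratio | Empirical SD ratio |
|---|---|---|---|
| 0.09 | 0.996 | 0.995 | 0.997 |
| 0.22 | 0.975 | 0.974 | 0.970 |
| 0.37 | 0.928 | 0.926 | 0.928 |
| 0.54 | 0.843 | 0.841 | 0.839 |
| 0.72 | 0.693 | 0.690 | 0.703 |

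Rejection under the null at two-sided 0.025 was 0.024 to 0.030 both with and without the covariate (Monte Carlo SE about 0.003). A separate two-arm simulation with many zero counts (4000 runs, raw correlation about 0.76) gave 2.5% without and 2.6% with, and a variance ratio of 0.42, as 1 - 0.76² = 0.42 predicts. The formula therefore holds for skewed counts, and type 1 error is kept either way. None of this estimates rho.

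**The case against.** The strongest reply is that this is an optimisation of unknown size. Protocol and SAP agree, and the absence of a covariate is stated openly. The change history suggests some thought: SAP version 2 dropped the change-from-OP wording from this dependent variable, and Protocol version 5 revised its statistical sections with reference to covariate-adjustment guidance. A rationale could sit in the Core SAP, which is not among the documents. With no rho, SD or effect on record, nobody can show that the endpoint is underpowered. The hierarchy consequence needs four earlier successes and then a miss that adjustment would have averted.

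All of that bears on the size, and it stands: confidence is high that the value is omitted, not that the omission will matter. It does not supply a reason for leaving the value out.

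A second point concerns validity. The simulations use complete months. The plan drops diary data after study drug discontinuation and sets aside months with fewer than 14 diary days. Validity then rests on the plan's own assumption (SAP 3.2) that discontinuers resemble continuers in the same arm and stratum. If missingness also depends on OP medication use, the omission could cost more than precision. That qualifies the word valid, and it argues for the covariate.

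A third point is cost. Under Protocol 12 an amendment needs ethics approval before it is implemented and goes to the regulators. The SAP is already at version 7 (25-Oct-2024), and the documents do not show whether the database lock has passed. This is fair: the programming is trivial, the paperwork is not.

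**Conclusion.** The concern holds. The fourth key secondary endpoint leaves out a pre-treatment measurement that is recorded daily, present for every subject analysed and already planned for a table, and neither document says why. The planned comparison is unbiased and keeps its type 1 error under randomization, with complete data or under the plan's own missing-data assumption. What it gives up is precision: an SE larger by a factor of 1/sqrt(1 - rho²), equivalent to 18, 50 and 98 of 200 subjects per arm at rho 0.3, 0.5 and 0.7, and negligible at 0.2 or below. These sizes rest on an assumed rho and the planned 200 per arm. The change should be made but is not essential, because the test stands without it. The unwritten OP formula is a minor editorial gap.

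**What to change.** Before unblinding at the last-subject-last-visit database lock (SAP 2.3):

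- Add OP acute migraine-specific medication days per month as a continuous covariate in Protocol 9.3.1.2 and SAP 6.3.2.2. Keep the on-treatment count as the dependent variable, and keep the sandwich SE.
- Write the OP derivation into SAP 6.3.2.2: 28 × (OP acute migraine-specific medication days)/(OP eDiary efficacy data days), over the OP analysis period of SAP 7.2. This has the same form as the OP migraine-day formula in SAP 6.3.1, and it also serves the table in SAP 6.2.5.2.
- Carry the term into the by-stratum models of SAP 6.3.2.2 and, with the analogous OP value, into exploratory SAP 6.3.3.6.

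Cost: one model term and one formula, from data already collected, with no subject lost, plus a SAP revision and a protocol amendment under Protocol 12.

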9.3.1.3 Multiplicity Correction

Type 1 error is controlled by splitting the alpha level between the 2 rimegepant treatment groups and the use of hierarchical testing. The significance of the primary endpoint for each treatment group is evaluated at a 2-sided alpha level of 0.025. If the primary endpoint is significant for a treatment group, then the secondary efficacy and outcomes research endpoints for that treatment group will be tested hierarchically, each at a 2-sided alpha level of 0.025, in the following order:

- Proportion of subjects with ≥ 50% reduction from the Observation Phase in the number of moderate to severe migraine days per month over the entire Double-blind Treatment Phase (Weeks 1 to 12).
- Mean change from the Observation Phase in the number of migraine days per month in the last 4 weeks (Weeks 9 to 12) of the Double-blind Treatment Phase.
- Mean change from the Observation Phase in the number of migraine days per month in the first 4 weeks (Weeks 1 to 4) of the Double-blind Treatment Phase.
- Mean number of acute migraine-specific medication days per month over the entire Doubleblind Treatment Phase (Weeks 1 to 12). Acute migraine-specific medications are triptans and ergotamine.
- Mean change from baseline in the MSQ restrictive role function domain score at Week 12 of the Double-blind Treatment Phase.

9.3.2 Safety Analyses

Deaths will be listed regardless of onset for the enrolled analysis set.

The frequencies of safety endpoints will be assessed descriptively as the number and percentage of subjects with events/findings separately for the 3 safety analysis sets.

The frequencies of the following safety endpoints will be tabulated on treatment: AEs by intensity (mild, moderate, severe, total); AEs by relationship to study drug (related, possibly related, unlikely related, not related); SAEs; AEs leading to study drug discontinuation; hepatic-related AEs by intensity; hepatic-related AEs leading to study drug discontinuation; laboratory test abnormalities by toxicity grade; and LFT elevations based on fold changes above ULN, including ALT or AST > 3x ULN concurrent (on the same laboratory test collection date) with total bilirubin > 2x ULN.

The investigators will determine the intensity of AEs and the relationship of AEs to study drug. The investigators' terms will be coded using the latest version of the Medical Dictionary for Regulatory Activities (MedDRA). AEs will be tabulated by system organ class and preferred term. In tables by intensity, if a subject has an AE with different intensities over time, then only the greatest intensity will be reported. In tables by relationship to study drug, if a subject has an AE with different relationships over time, then the highest degree of relatedness to study drug will be reported.

Laboratory test results will be graded according to numeric laboratory test criteria in Common Terminology Criteria for Adverse Events (CTCAE) Version 5.0 (2017), if available. Otherwise, if CTCAE grades are not available, then results will be graded according to numeric laboratory test criteria in Division of AIDS (DAIDS) Table for Grading the Severity of Adult and Pediatric Adverse Events Corrected Version 2.1 (2017). If a subject has a laboratory test abnormality with different toxicity grades over time, then only the highest toxicity grade will be reported.

In addition, Quality Tolerance Limits (QTLs) are predefined parameters that are monitored during the study. Important deviations from the QTLs and any remedial actions taken will be summarized.

9.4 Schedule of Analyses

There is 1 planned database lock at the end of the study. The final clinical study report will be produced to support regulatory requirements after the database lock at the end of the study. No interim analysis is planned.

10 ETHICS AND RESPONSIBILITIES

10.1 Good Clinical Practice

This study will be conducted in compliance with the protocol, Good Clinical Practice (GCP), Good Laboratory Practice (GLP), International Conference on Harmonization guidelines, and all applicable regulations, including the Federal Food, Drug and Cosmetic Act, U.S. applicable Code of Federal Regulations (title 21), any Independent Ethics Committee (IEC) requirements relative to clinical studies. The study will also be conducted in compliance with the recommendations laid down in the most recent version of the Declaration of Helsinki. This study will be conducted in compliance with the protocol. The protocol and any amendments and the subject informed consent will receive Institutional Review Board/Independent Ethics Committee (IRB/IEC) approval/favorable opinion prior to initiation of the study.

The Sponsor is responsible for ensuring that all updated relevant information related to the protocol be submitted to regulatory authorities and Independent Ethics Committees in accordance with local laws and regulations. This includes expedited reporting of suspected unexpected serious adverse reactions per regulatory guidelines.

All serious breaches must be reported to Pfizer (or designee) immediately. A Serious breach is a breach of the conditions and principles of GCP in connection with the study or protocol, which is likely to affect, to a significant degree, the safety or physical or mental integrity of the subjects of the study or the scientific value of the study.

Study personnel involved in conducting this study will be qualified by education, training, and experience to perform their respective task(s).

This study will not use the services of study personnel where sanctions have been invoked or where there has been scientific misconduct or fraud (e.g., loss of medical licensure, debarment).

It is the Sponsor's responsibility to submit the protocol and its amendments (if any), and the ICFs to regulatory authorities when necessary.

